9.2.1.2 Study Duration and Accrual

Participants will be screened approximately 75 days prior to vaccination and will be followed for 168 days after vaccination. The total study duration from screening to completion of follow-up per participant will be approximately 33.5 weeks (~8.4 months). We will recruit and screen up to 40 participants to obtain 24 participants with evaluable data to study. Given the focus of this study is on safety and potential adverse events, accrual will be staggered such that enrollment and treatment administration will include a maximum of 1 participant per week.

9.2.1.3 Randomization

Following enrollment, the 24 study participants will be randomly assigned to receive one vaccination with either **M3** (n=7), **M4** (n=7), **M3+M4** (n=7) or placebo (n=3) through a blinded randomization schedule.

9.2.1.4 *Un-blinding procedures*

Un-blinding of an individual participant is indicated in the event of a medical emergency where the clinical management would be altered by knowledge of the group assignment. The decision to un-blind will be taken in conjunction with the independent members of the SMC. Procedures and contact details for un-blinding procedures will be held in a site-specific SOP. The site study personnel will ensure that the reasons for un-blinding are documented in the CRF.

All study participants will be un-blinded when the last vaccinated participant has completed the Day 28 Visit and the second leukapheresis.

9.3 Statistical Analyses

9.3.1 *General Approach*

We plan a double blind, randomized, placebo-controlled, parallel design study to evaluate the safety and immunogenicity of viral-vector, MVA, expressing immunogens, tHIVconsV3 (**M3**) and tHIVconsV4 (**M4**), derived from conserved yet immunogenic regions of HIV-1. The study population is HIV-1 infected adults on c-ART with plasma HIV-1 RNA <50 copies/mL.

Participants will be randomized to receive **M3** or **M4** alone, **M3+M4** together, or placebo at Day 0 and continue baseline ART. At Day 28, all participants undergo a 2nd leukapheresis to evaluate for an increase in the breadth of T cells targeting conserved regions of HIV-1. Unblinding will occur after the last participant has completed the Day 28 visit and leukapheresis. Participants will be followed for safety assessments through Day 168.

9.3.2 *Immunological and Virologic Analysis*

Given the small sample size in this study, exact methods that do not rely on large sample assumptions will be used for statistical inference and will always be presented with corresponding descriptive statistics and/or data visualization. Because this is a Phase 1 study with a small sample size and exploratory endpoints, results will be presented without adjustment for multiple hypothesis testing; a statistical significance level of 0.05 will be used. Whenever feasible, data visualization will present individual-level data points as well as summary statistics. Emphasis will be placed on estimated effect sizes and descriptive summaries. The sample size was chosen to evaluate safety and the primary efficacy outcome; this study includes a small total number of participants and thus may not detect all scientifically meaningful effects at a .05 statistical significance level. All study results should be interpreted within the context of the study eligibility criteria and the population available and willing to participate in this double-blinded, placebo-controlled randomized clinical trial.

9.3.3 Analysis of the Primary Endpoint(s)

The probability of a primary safety event through Day 28 following vaccination will be estimated with a proportion and a corresponding 95% 1-sided exact binomial upper confidence limit.

9.3.4 Analysis of the Secondary Endpoint(s)

9.3.5 Immunological and Virologic Analysis

To evaluate changes in HIV-1 epitope-specific CD8⁺ T cell responses detected in IFN- γ ELISpot assays before and after vaccination, the relative change within participants (from Day 0 to both Day 7 and Day 14) will be estimated using a geometric mean ratio and evaluated with an exact 2-sided Wilcoxon signed-rank test. If the symmetry assumption for change in natural log-transformed summed HIV-1 specific T cell response appears violated, a sign test will be conducted as a sensitivity analysis. Efficacy and exploratory endpoints defined as a proportion of participants will be analyzed with a 2-sided binomial 95% CI. Within a vaccination arm, changes in continuous measurements over time (e.g., change in an immune parameter from baseline to post-vaccination) will be summarized graphically and evaluated with an exact 2-sided Wilcoxon signed-rank test, or a sign test for endpoints that appear to violate assumptions of the Wilcoxon test.

Observed immunologic measurements, such as the change in breadth following vaccination, may not be normally distributed or may be partially censored due to assay limits of quantification, and thus, an exact Wilcoxon rank-sum test will be used for between-arm comparison.

The focus of our **secondary** objectives is to examine the effect of vaccination on within-participant T cell magnitude and between-arm breadth of HIV-specific T cell responses.

9.3.6 T cell Magnitude:

The primary *within arm* outcome will be the summed HIV-specific T cell response, either to peptides pools spanning the immunogen or pools of optimal HIV CD8⁺ epitopes. HIV specific T cell responses will be measured at baseline, Day 7, and Day 14 (following **M3, M4, or M3+M4** vaccination). An average fold change of at least 2 (comparing T cell responses within participant) was anticipated to be scientifically meaningful. The specific alternative hypothesis is a geometric mean ratio (GMR) of 2. The assumed between-participant standard deviation (SD) for natural log-transformed HIV-specific T cell response was estimated from previous baseline data derived from HIV-infected participants durably suppressed by ART sampled weekly or monthly. Data were provided by [name] (66). Empirical power for the exact Wilcoxon signed-rank test was calculated using 100,000 simulated datasets assuming natural log-transformed HIV-specific T cell

response follows a normal distribution, and the effect size under the alternative hypothesis was a GMR of 2 on the raw HIV-specific T cell response measures. A between-participant SD of 0.8 at baseline was observed using log-transformed HIV-specific T cell response from previous baseline data; the same SD for both pre-vaccination and post-vaccination measurements was assumed to calculate power. The estimated correlation within a participant was >0.9 between paired log-transformed HIV-specific T cell response measures. Using a 2-sided exact Wilcoxon signed-rank test and a 0.05 significance level, n=7 vaccinated participants provides >95% power to detect a GMR of 2 or greater for a pre- and post-vaccine paired measurement correlation of 0.9 and a between-individual SD of 0.8. For a smaller within-individual correlation of 0.8 and the same assumptions otherwise, the estimated power is 82%.

Comparison of peak HIV specific T cell responses *between* arms (**M3+M4** vs **M3**, **M3+M4** vs **M4**) will be compared using a 2-sided exact Wilcoxon rank-sum test. With n=7 per vaccination group it is possible to achieve an exact p-value <0.05. Assuming a 90% probability that the peak HIV specific T cell responses for any given participant in the **M3+M4** arm is higher than for any given individual in the **M3** arm, there is >80% power to detect a difference between arms. This same power calculation applies for the **M3+M4** vs **M4** comparison. Power for the exact Wilcoxon rank-sum test was calculated in R version 3.4.3 using the *wmwpow* package.

9.3.7 T cell Breadth:

Observed immunologic measurements, such as the change in breadth following vaccination, may not be normally distributed, and thus, a 2-sided exact Wilcoxon rank-sum test will be used for comparisons between arms.

We anticipate zero change in T-cell breadth for the **M3** and **M4** arms. For the **M3+M4** arm, we anticipate change of breadth ranging from 0-6 epitopes ([Table 13](#)). Data in [Table 13](#) describes the distribution of HIV-specific T-cell responses identified in 20 HIV-infected, durably suppressed participants provided by [name].

Table 13 Distribution of Regions of HIV Epitopes Targeted by T-Cells in HIV-1 Infected Participants Durably Suppressed with ART

# Epitopes found in tHIVconsvX	% distribution
0	15
1	15
2	30

3	20
4	5
5	10
6	5

Given the assumptions in [Table 13](#) and above (zero change in T cell breadth for the M3 and M4 only arms), n=7 evaluable participants per arm provides >90% power to detect a difference between arms (M3+M4 vs M3, M3+M4 vs M4) using a 2-sided exact Wilcoxon rank-sum test and a 0.05 significance level.

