3 OBJECTIVES AND ENDPOINTS

OBJECTIVES	ENDPOINTS	JUSTIFICATION FOR ENDPOINTS
Primary		
Evaluate the safety of vaccination with M3 or M4 or M3+M4 in HIV-1 infected participants on ART with plasma HIV-1 RNA <50 copies/mL.	Safety Occurrence of at least one \geq Grade 3 Adverse Event (AE) including signs/symptoms, lab toxicities, and/or clinical events, that is possibly or	The study will use standard safety grades used in HIV clinical trials. If exceeded, it is currently felt that such risks would be

OBJECTIVES	ENDPOINTS	JUSTIFICATION FOR ENDPOINTS
	
definitely related to study treatment any time from the first day of treatment through 28 days following vaccination. Safety data will include local and systemic signs and symptoms, laboratory measures of safety/toxicity, and all adverse and serious adverse events. Safety data will be routinely collected throughout the duration of the study.
 
NOTE: The occurrence of a Grade 3 elevated blood pressure during a study-related leukapheresis that resolves following completion of the procedure will not be included as a primary safety endpoint.
	unacceptable in a research study of this nature.

OBJECTIVES	ENDPOINTS	JUSTIFICATION FOR ENDPOINTS
Secondary		
Evaluate the safety of vaccination with M3 or M4 or M3+M4 in HIV-1 infected participants on ART with plasma HIV-1 RNA <50 copies/mL.	Occurrence of any \geq Grade 1 AE including signs/symptoms, lab toxicities, and/or clinical events, that is possibly, probably, or definitely related to study treatment any time from the first day of treatment through Day 168 (Week 24) following vaccination.	
Compare the within-participant relative change in magnitude of HIV-1-specific T cell responses in participants following vaccination with either M3 or M4 or M3+M4 .	Relative changes in magnitude of T cell responses to HIV-1 conserved regions measured by ex vivo IFN- γ ELISpot from pre-vaccination on Day 0 to post-vaccination on Day 7 and 14.	Previous studies indicate that the rMVA-induced T cell response, typically measured by ex vivo IFN-γ ELISpot, peaks between day 7-14 days following vaccination.

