7 STUDY INTERVENTION DISCONTINUATION AND PARTICIPANT DISCONTINUATION/WITHDRAWAL

7.1 Discontinuation of Study Intervention

Premature Treatment Discontinuation Evaluations

There is only one study treatment intervention visit at Day 0. The collection of safety labs, virologic, immunologic, SCA, and the 2nd leukapheresis will continue to be collected per SOE, section 1.3.

Participants who complete the vaccine/placebo injection but do not complete the Day 7 study visit will be replaced, provided the inability to complete the Day 7 visit is not due to a study-related AE.

Participants who complete the vaccine/placebo injection but do not complete the Day 28 study visit and 2nd leukapheresis procedure will be replaced, provided the inability to complete the Day 28 visit is not due to a study-related AE.

Participants who receive vaccine/placebo but are unable to complete the Day 7 or 2nd leukapheresis should be encouraged to continue on study for safety assessments per the SOE.

Discontinuation of Antiretroviral Therapy

If the participant discontinues ART prior to DAY 0, DO NOT give the vaccine/placebo injection. DO NOT collect research labs for the time points after the participant discontinued ART. This participant will be replaced.

If the participant discontinues ART after the vaccine or placebo administration (Day 0), the participant should continue on study for safety follow-up as noted in the SOE. Collection of virologic, immunologic, SCA, and the 2nd leukapheresis samples will be determined on a case-by-case basis in discussion with the protocol team. This participant may be replaced.

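### The between-arm T-cell magnitude test uses peak response with no Day 0 term; a Day 0-adjusted exact rank-sum test would be a cheap gain in efficiency

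*Combined protocol and SAP*

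**What the plan says.** Section 9.3.6 sets out a "Comparison of peak HIV specific T cell responses" for M3+M4 against M3 and M3+M4 against M4, using a 2-sided exact Wilcoxon rank-sum test. The power statement begins "Assuming a 90% probability that the peak HIV specific T cell responses for any given participant in the" combination arm exceeds that of a participant in the single-vaccine arm, and claims more than 80% power with 7 per arm. No baseline term, change score or scale is given, and peak is not defined. Section 3 says only that the response "peaks between day 7-14 days following vaccination".

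Elsewhere magnitude is referred to Day 0. The secondary endpoint in Sections 1.1 and 3 is relative change from Day 0. For the within-arm analysis, Section 9.3.5 says "the relative change within participants (from Day 0 to both Day 7 and Day 14) will be estimated using a geometric mean ratio". Its power in Section 9.3.6 is quoted "for a pre- and post-vaccine paired measurement correlation of 0.9 and a between-individual SD of 0.8", with 0.8 as the lower correlation. The SD was "estimated from previous baseline data derived from HIV-infected participants durably suppressed by ART sampled weekly or monthly", and "the same SD for both pre-vaccination and post-vaccination measurements was assumed to calculate power".

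**The concern.** Section 4.1 hypothesises a greater total magnitude with M3+M4 than with either vaccine alone, and this rank-sum test is the one named for that comparison. The plan assumes that a person's Day 0 response predicts most of the variation in the later response, but uses this only within arms. Between arms, the spread of people's starting levels stays in the comparison as noise. With 7 per arm fixed, that could hide a difference which the same samples, compared relative to Day 0, would show. Two details are also open and could be settled after seeing data: which day counts as peak, and which of the two peptide-pool sums in Section 9.3.6 is used.

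**Working it through.** **Inputs from the plan (Sections 9.3.2 and 9.3.6).** 7 against 7; 2-sided alpha 0.05; natural-log SD 0.8 before and after vaccination; paired correlation r = 0.9, or 0.8 as the lower case; P(X>Y) = 0.90 for the between-arm power.

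**Assumptions added here.** Normal log responses; equal correlation among Days 0, 7 and 14; peak is the larger of Days 7 and 14; a between-arm ratio of 2 as an illustration.

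**Step 1: the plan's own figures.** The exact test rejects at U ≤ 8 or U ≥ 41, with size 0.0379. Simulated power at P(X>Y) = 0.90 is 81.8% for normal data, 81.0% for exponential and 80.3% for Laplace, so the stated figure of more than 80% holds. The within-arm signed-rank figures also reproduce: 97.9% at r = 0.9 (plan: above 95%) and 82.3% at r = 0.8 (plan: 82%).

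**Step 2: what P(X>Y) = 0.90 means on raw response.** For normal logs, P(X>Y) = Φ(log g / (SD × √2)), so g = exp(1.2816 × √2 × 0.8) = exp(1.45) = 4.26. A 2-fold difference gives P(X>Y) = 0.73.

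**Step 3: noise removed by Day 0.**
- Raw peak on one day: SD 0.80.
- Simple change, 0.8 × √(2(1 − r)): 0.358 (r = 0.9), 0.506 (r = 0.8).
- Regression on Day 0, 0.8 × √(1 − r²): 0.349 (r = 0.9), 0.480 (r = 0.8).

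**Step 4: simulated power at a 2-fold difference, larger of two days.** Adjusted means the exact rank-sum test on residuals of log peak on log Day 0, fitted in the 14 participants with arm ignored.

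| Correlation | Raw peak | log(peak/Day 0) | Adjusted |
|---|---|---|---|
| 0.9 | 27% | 92% | 88% |
| 0.8 | 28% | 65% | 65% |
| 0.5 | 31% | 31% | 38% |

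Raw against adjusted is 29% and 51% at r = 0.7, 33% and 33% at 0.3, and 37% and 34% at 0. Simulated size is 0.037-0.039 for all three tests. The residuals are computed without arm, so under the null they do not change when labels are permuted.

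**Step 5: difference detectable with 80% power.** Raw peak: about 4-fold. Adjusted: about 1.85-fold (r = 0.9) or 2.3-fold (r = 0.8).

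**Step 6: sensitivity (all assumptions).**
- Log fold response varies between people with SD 0.5: raw 20-21%; adjusted 40% (0.9) or 33% (0.8).
- Vaccine adds a fixed amount, 3 against 1 baseline medians: raw about 79%, adjusted about 95%, simple change 45% (0.9); 72%, 83% and 37% (0.8); 54%, 53% and 25% (0.5).
- Day 14 missing for one person per arm, with Day 7 used: adjusted 87% (0.9) or 63% (0.8).
- Day 0 at the assay limit for 15% of values: adjusted 84% (0.9) or 62% (0.8); for 30%, 76% or 58%.

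**The case against.** The comparison is peripheral. The hypotheses in Section 9.1 claim superiority of M3+M4 for breadth only, and Section 9.3.5 puts the secondary focus on within-participant magnitude and between-arm breadth. Section 9.3.2 stresses effect sizes and description, and concedes that meaningful effects may be missed. All of this stands, and it limits the weight of the point.

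The headline gain depends on a correlation from baseline samples without vaccination. That stands too: Step 6 shows the contrast falling to 20-21% against 33-40% under varied responses. The downside is small, though: adjustment costs about 3 to 4 points even at zero correlation.

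Simple log(peak/Day 0) matches the endpoint, carries a fold unit and does as well or slightly better on the plan's own inputs. It is an acceptable alternative. Its weakness is that it falls below raw peak when the correlation is under about 0.5 (equal SDs), or when the boost is additive.

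Three stronger readings are tempting. A reader might infer that the planned test is invalid or its power misstated; Step 1 shows neither. A reader might infer that the plan misses its own 2-fold target; that target is for within-participant change, and no between-arm fold is set. A reader might also put the residual SDs of Step 3 into the Step 2 formula and say that P(X>Y) = 0.90 becomes 1.9-fold (0.9) or 2.4-fold (0.8) after adjustment. That uses the true slope. A slope fitted with arm ignored absorbs part of the arm effect, so at 1.88-fold and 2.39-fold on one day P(X>Y) is about 0.883 and power about 76%.

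**Conclusion.** The point holds as a cheap improvement to a valid, correctly powered, supportive comparison. At the plan's SD and correlation, Day 0 adjustment raises power at an illustrative 2-fold difference by 37 points (65% against 28%, correlation 0.8) to 61 points (88% against 27%, correlation 0.9). This rests on log-normal responses, equal SD before and after vaccination, a correlation that carries over from unvaccinated samples, and peak taken as the larger of two days. Where those fail, the gain is smaller, and near or below a correlation of 0.3 it is nil or slightly negative. The documents do not support calling this an error in the test, in its power or in a listed secondary endpoint.

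**What to change.** Amend Section 9.3.6 before unblinding, which Section 9.2.1.4 ties to the last participant's Day 28 visit and second leukapheresis:

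- **Peak.** Define it as the larger of the Day 7 and Day 14 summed responses, using the same single sum as the within-arm test. If one day is missing, use the other. Day 7 should seldom be missing, since Section 7.1 says "Participants who complete the vaccine/placebo injection but do not complete the Day 7 study visit will be replaced", except when a study-related adverse event is the cause.
- **Test.** For each comparison, regress log peak on log Day 0 in the 14 participants with arm ignored, and apply the exact 2-sided rank-sum test to the residuals.
- **Limits and ties.** Set values at or below the assay limit to that limit, and use mid-ranks for ties.
- **Reporting.** Give log(peak/Day 0) as a ratio of geometric mean ratios, and raw peak, descriptively only.
- **Power sentence.** Add that P(X>Y) = 0.90 on raw response at SD 0.8 is about 4.3-fold. Attach no fold figure at P(X>Y) = 0.90 to the adjusted test.

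If the statisticians prefer simple log(peak/Day 0), they should name it as the single test in advance.

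The cost is wording: no new samples, visits or participants. The trade-offs are about 4 points less power than simple change at correlation 0.9, about 3 to 4 points less than raw peak if the correlation is near 0, and residuals without a fold unit, which is why the descriptive ratio must accompany the p-value.

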9.3.8 Safety Analyses

For the safety endpoints, we will describe all study treatment-related AEs through Day 28 (primary endpoint) and the end of study (secondary endpoint). AEs will be coded per the Medical Dictionary for Regulatory Activities (MedDRA). Events prior to treatment (e.g., due to study-related procedure) will be listed separately in an appendix to the final clinical study report. The following tables of AE data will be created to summarize the number and percent of participants who experience at least one event of each of the following types:

- Study treatment-related AEs by severity grade
- All SAEs (this may be a listing if there are few events)
- Study treatment-related SAEs
- Fatal AEs (this may be a listing if there are few events)
- AEs that result in study discontinuation or study treatment discontinuation
- AEs categorized as AESI
- AEs with severity Grade 3 or greater
- Study treatment-related AEs with severity Grade 3 or greater
- All treatment-related AEs with severity Grade 1 or greater

All of these tables will display the number and percent of participants that experience the given event and will display events by System Organ Class (SOC) and Preferred Term (PT). Events will be displayed alphabetically for SOC and in descending order of overall PT incidence within each SOC.

9.3.9 *Tabulation of Individual Participant Data*

Individual participant data will be listed by measure and time point.

9.3.10 *Exploratory Analyses*

Other objectives or exploratory analysis can be grouped into additional immunological measures and virologic measures.

Immunologic measures: Kinetic data will be analyzed by descriptive statistics and graphical displays. Other observed immunologic measurements such as virus inhibition may not be normally distributed or may be partially censored due to assay limits of quantification, and thus, an exact Wilcoxon signed-rank test will be used for within-participant comparisons.

Virologic measures: Virologic measures such as cell-associated HIV-1 RNA will be log-transformed prior to analyses. Appropriate analysis method will be used for plasma HIV-1 RNA by SCA depending on the amount of results below assay limit. For example, if a substantial fraction (~50%) are below the assay limit, the analysis will focus on estimating the proportion of participants with detectable SCA at various time points and comparison between arms will use Fisher's exact test; otherwise, changes within participants will be summarized and compared between arms using Wilcoxon rank-sum tests.

10 SUPPORTING DOCUMENTATION AND OPERATIONAL CONSIDERATIONS

10.1 Regulatory, Ethical, and Study Oversight Considerations

10.1.1 *Informed Consent Process*

10.1.1.1 *Consent/assent and Other Informational Documents Provided to Participants*

Consent forms describing in detail the study intervention, study procedures, and risks are given to the participant and written documentation of informed consent is required prior to any screening procedures and prior to starting study intervention/administering study intervention.

10.1.1.2 *Consent Procedures and Documentation*

Informed consent is a process initiated prior to individuals agreeing to participate in the study and continues throughout the individual's study participation. The consent forms are UNC IRB -approved and the participant will be asked to read and review the document. The study investigator (or designee) and/or study coordinator will explain the research

study to the participant and answer any questions that may arise. A verbal explanation will be provided in terms suited to the participant's comprehension of the purposes, procedures, and potential risks of the study and of their rights as research participants. Participants will have the opportunity to carefully review the written consent form and ask questions prior to signing. The participants are provided the opportunity to discuss the study with their family, primary care provider, or significant other or to just think about the study and its requirements prior to agreeing to participate. The participant signs the informed consent document prior to any procedures being done specifically for the study. Participants are informed that participation is voluntary and that they may withdraw from the study at any time, without prejudice. A copy of the informed consent document will be given to the participants.

The informed consent process will be conducted and documented in the source document, and the consent form signed, before the participant undergoes any study-specific procedures. The study PI (or designee) or the research coordinator will inform participants that the quality of their medical care will not be adversely affected if they decline to participate in this study, thus emphasizing the protection of the rights and welfare of the participants.

